9.4.2.1 Primary Endpoint

The primary efficacy endpoint for Part 2 (Main Cohort) is the change from baseline in pre-bronchodilator FEV₁ at Week 4 compared to placebo.

The change from baseline in FEV₁ will be analysed using MMRM with treatment group, week (1 to 4), country, eosinophil count group (< 300, \geq 300 cells/ μ L), baseline FEV₁, and treatment-by-week interaction as fixed effects with participant as random effect. In this model, Week 1 to 4 corresponds to Visit 4 to 7. The within-participant correlation will be modelled using the unstructured covariance matrix. The Kenward-Roger approximation will be used to estimate the degrees of freedom.

Baseline for FEV₁ will be defined as the mean of the 2 measured values before first study intervention administration (30 minutes apart, at -45 minutes and -15 minutes, before study intervention) on Day 1.

Besides the main analysis in the FAS, treatment effect in primary endpoint will be evaluated in subgroups defined by measurements of eosinophil count (< 300 and \geq 300 cells/ μ L), and of FeNO (< 50 and \geq 50 ppb) evaluated at Day 1 pre-dose.

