4.10.1 Analysis and Data Conventions

No statistical hypotheses will be tested in Part 1 (Lead-in Cohort) of this study. Part 2 (Main cohort) of this study aims to demonstrate that AZD1402 improves FEV₁ compared to placebo.

The null hypotheses for the primary analysis in Part 2 is that there is no difference in the change from baseline at Week 4 (Visit 7) in pre-bronchodilator in-clinic FEV₁ in AZD1402 treated participants compared to placebo-treated participants.

The following comparisons will be performed:

- AZD1402 inhalation ^{CCI} mg ^{CCI} versus placebo inhalation ^{CCI}.
- AZD1402 inhalation ^{CCI} mg ^{CCI} versus placebo inhalation ^{CCI}

4.10.2 No formal comparisons between the different AZD1402 doses will be conducted. Adjustments for Covariates

The primary efficacy analysis for Part 2 will be adjusted for the following baseline covariates:

1. Country (stratification variable)
2. Baseline FEV₁

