4.11 Primary Efficacy Variable (Part 2)

The primary variable for the assessment of efficacy for Part 2 is the change from baseline pre-bronchodilator in-clinic FEV₁ at Week 4.

The change from baseline in pre-bronchodilator FEV₁ will be analysed using MMRM with treatment group, week (1 to 4), country, baseline FEV₁, and treatment-by-week interaction as fixed effects and with participant as random effect. In this model, Week 1 to Week 4 corresponds to Visit 4 to Visit 7.

The within participant correlation will be modelled using the unstructured covariance matrix. The Kenward-Roger approximation will be used to estimate the degrees of freedom. The REML method will be applied.

If the estimating algorithms will not converge, the following steps will be taken to simplify the model until convergence is achieved:

1. As a first step, try in order these 3 covariance structures: Toeplitz, the first-order autoregressive, and compound symmetry. Stop as soon as convergence is achieved.

Statistical Analysis Plan

2. If step 1 does not work, the treatment-by-week interaction will be removed from the last model in step 1, ie, from the model with compound symmetry.
3. In case non-convergence persists, the analysis will be changed to use the analysis of covariance (ANCOVA) instead of mixed-effects model for repeated measures.

Each treatment effect and treatment comparisons (all active treatments to placebo) will be estimated by the Least Square means (LS means) and the difference in LS means at the corresponding week (Week 1, Week 2, Week 3, Week 4) on the treatment-by-week interaction, along with their standard errors (SE) and 95% CIs, and the p-value corresponding to the between-treatment group difference. A plot showing the LS mean change (+/- SE) from baseline in FEV₁ over time within each treatment group will be provided.

Missing values will not be imputed. In this analysis it is thus assumed that any missing FEV₁ values are missing at random.

A listing of the primary efficacy data will be provided based on the FAS.

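### SAP 4.11 fallback step 2 drops treatment-by-week, so if that step is reached the Week 4 primary effect is replaced by a common Weeks 1–4 effect

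*SAP*

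**What the plan says.** SAP 4.11 names the primary variable as "the change from baseline pre-bronchodilator in-clinic FEV₁ at Week 4", and the null hypothesis in SAP 4.10.1 is also set at Week 4. The planned model has treatment, week, country, baseline FEV₁ and "treatment-by-week interaction as fixed effects and with participant as random effect". The next paragraph adds: "The within participant correlation will be modelled using the unstructured covariance matrix".

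If the model does not converge, three steps follow.

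1. Change the covariance: "try in order these 3 covariance structures: Toeplitz, the first-order autoregressive, and compound symmetry. Stop as soon as convergence is achieved". The interaction stays in the model.
2. If all three fail, "the treatment-by-week interaction will be removed from the last model in step 1", that is, from the compound-symmetry model.
3. If that also fails, replace the mixed model by an ANCOVA. Its response is not stated.

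After these steps, SAP 4.11 says that the treatment comparisons are LS-mean differences by week, taken from the treatment-by-week interaction. SAP 4.12.1 defines the secondary endpoint, the average over the treatment period, as the LS-mean difference on the treatment factor of the same model.

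Protocol 9.4.2.1 gives the same random-effect wording ("treatment-by-week interaction as fixed effects with participant as random effect") with an unstructured covariance, but has no fallback steps.

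**The concern.** Step 2 removes the term that carries the primary contrast. Without it, the Week 4 difference is constrained to equal the difference at every other week. Three statements can then no longer be met as written: the primary variable, the null hypothesis, and the sentence that reads the comparisons by week from the interaction. The primary result and the secondary four-week average become the same number. An analyst who follows the rule exactly could report a four-week average as the Week 4 result.

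Step 3 does not close the gap, because it does not say whether the ANCOVA response is Week 4 or an average.

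A second, separate matter is the wording of the covariance model. The text names a participant random effect and also an unstructured within-participant matrix. If both are fitted, one parameter is redundant, and the planned covariance could be abandoned because of the coding and not because of the data.

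**Working it through.** **The plan's own figure.** The only stated calculation is the sample size in SAP 4.19: 73 evaluable per arm for 175 mL, one-sided 5%. Power and SD are redacted, so it cannot be reproduced. With n = 2(z₁₋α + z₁₋β)²SD²/δ², 73 per arm fits an SD of about 425 mL at 80% power or 361 mL at 90%. Nothing below depends on it.

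**What step 2 estimates.** Let d₁ to d₄ be the true treatment differences at Weeks 1 to 4. With the interaction, the Week 4 contrast estimates d₄. Without it, under compound symmetry and complete data, the single treatment coefficient is (d₁ + d₂ + d₃ + d₄)/4. A numerical fit of both models confirmed that this equality is exact. The documents give no weekly profile, so the profiles below are assumptions, each with d₄ = 175 mL.

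| Assumed profile | Arithmetic | Step 2 target | Against 175 mL |
|---|---|---|---|
| Constant | 4 × 175 / 4 | 175 mL | 0% |
| Linear build-up | (43.75 + 87.5 + 131.25 + 175) / 4 = 437.5 / 4 | 109.4 mL | −37.5% |
| Faster build-up | (75 + 125 + 150 + 175) / 4 = 525 / 4 | 131.25 mL | −25% |
| Waning | Weeks 1–3 sum to 690 (mean 230): (690 + 175) / 4 | 216.25 mL | +24% |

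A small simulation (80 per arm, assumed SD 400 mL and correlation 0.7, 60 datasets per profile) gave the following mean differences, step 2 estimate minus with-interaction Week 4 estimate, on complete data:

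- constant: −1.6 mL (SE 3.9)
- linear build-up: −65.6 mL (SE 3.9), against an expected 109.4 − 175 = −65.6
- waning: +40.4 mL (SE 3.6), against an expected 216.25 − 175 = +41.25

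With 10% dropout the differences were −4.6, −74.7 and +40.6 mL.

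**What a random intercept adds.** Let R be the 4 × 4 within-participant matrix, τ the random-intercept variance and J the matrix of ones. The data identify only V = R + τJ. Each structure is judged by whether R can absorb a constant added to every element.

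| Structure | Parameters with intercept | Rank | Identified |
|---|---|---|---|
| Unstructured | 10 + 1 = 11 | 10 | No |
| Toeplitz | 4 + 1 = 5 | 4 | No |
| First-order autoregressive | 2 + 1 = 3 | 3 | Yes |
| Compound symmetry | 2 + 1 = 3 | 2 | No |

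For the autoregressive case, write the lag values as v₀ = σ² + τ, v₁ = σ²ρ + τ and v₂ = σ²ρ² + τ. Then ρ = (v₁ − v₂)/(v₀ − v₁), σ² = (v₀ − v₁)/(1 − ρ) and τ = v₀ − σ², so all three parameters are recovered.

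REML fits (160 participants, three assumed true covariances, 12 datasets each) agree. With the random intercept, the unstructured, Toeplitz and compound-symmetry fits were singular in 36 of 36 each. The autoregressive fit was regular in 29 of 36, had τ at zero in 7 of 36, and was singular in none. Without the random intercept, all 4 × 36 = 144 fits were regular.

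**Order of the ladder.** If redundancy were the only problem, the sequence would go from unstructured through Toeplitz to autoregressive. It would stop there, with treatment-by-week still in the model.

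**The case against.** The strongest reply is that step 2 is remote. All four covariance structures must fail first, and all three alternatives in step 1 keep the Week 4 contrast. This stands. A reader might infer that any failure to converge loses the primary estimand, but the documents do not support that: only step 2 does so.

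A reader might also infer that the redundant random effect triggers the deletion. That is not supported either. The autoregressive model with a random intercept is identified and is tried before compound symmetry, so something else would have to make it fail. The redundancy itself depends on coding. The phrase "and with participant as random effect" may mean only that participant is the subject of the covariance, and the SAP gives no code. Nor is an unidentified parameter the same as non-convergence, since software may report convergence with a singular Hessian.

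Finally, the error need not dilute the effect. It is zero for a constant effect and inflates a waning one.

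What the reply does not answer is that, once reached, the written rule yields the wrong quantity and conflicts with the rest of its own section. It may not help convergence either. If compound symmetry fails because of an added random intercept, the fault lies in the covariance, and removing a fixed interaction does not repair it.

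**Conclusion.** The point holds in conditional form. If step 2 of SAP 4.11 is reached, the Week 4 primary difference is replaced by a common Weeks 1–4 effect, which is the secondary endpoint of SAP 4.12.1. That follows from the text alone. The size depends on assumed profiles: for 175 mL at Week 4, the target is about 109 mL under linear build-up, unchanged under a constant effect, and about 216 mL under the waning profile. The chance of reaching step 2 is low and cannot be quantified from the documents.

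The random-effect wording is a separate request for clarification. If a random intercept is fitted with the unstructured matrix, the model is not identified, which could cause an unnecessary departure from the planned covariance. The rank result needs no simulation assumptions, but whether it applies depends on how the model is coded. The change should be made because the rule is wrong as written and cheap to correct, not because the failure is likely.

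**What to change.** In SAP 4.11:

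- Keep treatment-by-week in every mixed model and delete step 2.
- If every structure in step 1 fails, go directly to an ANCOVA of the Week 4 change with treatment, country and baseline FEV₁. This also settles the unstated response in the present step 3.
- State that participant is only the subject of the repeated-measures covariance, with no added random intercept.

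SAP 4.12.4 analyses log FeNO by the method of 4.11, so the correction carries over to the Week 4 FeNO comparison.

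The cost is a few sentences in a new SAP version before database lock, which the SAP introduction already provides for. Protocol 9.4.2.1 has the same random-effect wording, so the clarification should be recorded in SAP 4.20 to explain the difference. There is no effect on participants or data collection. One small downside is that a Week 4 ANCOVA drops participants without a Week 4 value and so does not use their Week 1–3 data. A Week 4 version of the already planned step 3 would do the same.

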4.12 Secondary Efficacy Variables (Part 2)

4.12.1 Forced Expiratory Volume in One Second

The analysis of change from baseline in pre-bronchodilator in-clinic FEV₁ average over the treatment period will be conducted as part of the analysis for the primary endpoint as described in Section 4.11. The overall treatment effect and treatment difference over the 4-week treatment period will be estimated by the LS means and the difference in LS means on the treatment factor, along with the SEs, and 95% CIs and the p-value corresponding to the between-treatment group difference.

4.12.2 Asthma Control Questionnaire-6

A summary by treatment group (different doses of AZD1402, pooled AZD1402 and placebo) in terms of absolute values at baseline and average over the treatment period, as well as change from baseline and its average over the treatment period, will be presented for ACQ-6. Information from ACQ-6 assessments will also be listed. The average over the treatment period will be calculated from the subjects' average measurements of all assessments performed while subjects are on-treatment. Also, the number and percentage of participants with a decrease in ACQ-6 score of ≥ 0.5 (responders) over the treatment period for each treatment group will be described.

4.12.3 PEF and Asthma Symptoms Score

A summary by treatment group (different doses of AZD1402, pooled AZD1402 and placebo) in terms of absolute values at baseline and average over the treatment period, as well as change from baseline and its average over the treatment period, will be presented for average morning PEF, average evening PEF and in daily average asthma symptom score (AM/PM).

The average morning PEF will be calculated as:

(sum of morning PEF values in treatment period) / (number of morning e-Diary sessions completed during period).

The average evening PEF will be calculated analogously.

Statistical Analysis Plan

Daily asthma symptom score for day n will be the average of the evening score recorded for day n and the morning score for day n+1.

The average daily asthma symptom score will be calculated as:

(sum of daily values in treatment period) / (number of calculated daily values during period).

4.12.4 Fractional Exhaled Nitric Oxide

The analysis of change from baseline in log transformed FeNO will be performed as described for the primary endpoint in Section 4.11. These analyses will be done on the natural log scale and the results will be back-transformed to linear scale. Hence treatment effects will be presented in terms of Geometric LS means (GeoLSMeans) and treatment differences and associated CIs will be presented in terms of GeoLSMeans ratios. Due to the log-transformation, the GeoLSMeans represent a relative change from baseline rather than an absolute change from baseline.

Percentage change from baseline in FeNO at each week and average over the treatment period will be summarised by treatment group and the following summary statistics will be presented: n, geometric mean, GeoCV (%), median, minimum, and maximum.

For repeated follow-up post-baseline measurements that are taken on the same day and time as a scheduled visit and time point, the average response value of the morning assessments will be used. The average over the treatment period will be calculated from the subjects' average measurements of all assessments performed whilst subjects are on-treatment between Visit 3 and Visit 7.

All the efficacy variables will be presented in listings.

The following figures will be presented:

[figure not shown]
- In-clinic FeNO, individual subject data over time.
- Mean FeNO in-clinic absolute values (ppb) by week
- Mean FeNO in-clinic percentage change from baseline by week
- GeoLSMeans of the ratio (post/baseline) (+/- SE) in FeNO over time within each treatment group will be provided.

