9.4.2.2 Secondary Endpoints

Secondary efficacy endpoints for Part 2 (Main Cohort) will include:

- Change from baseline in pre-bronchodilator FEV₁ average over the 4-week Treatment Period
- Change from baseline in ACQ-6 at Week 4 and average over the Time Period
- Change from baseline in average morning PEF over the Treatment Period
- Change from baseline average evening PEF over the Treatment Period

- Change from baseline in daily average asthma symptoms score (AM/PM) over the Treatment Period
- Change from baseline in FeNO at Week 4 and average over the Treatment Period (analysed on natural log scale and results back transformed to linear scale).

Similar MMRM as for the primary variable will be used for analysis of change from baseline in ACQ-6 and in FeNO. Analysis of covariance with treatment and country as fixed effects, and baseline as covariate will be used for the analysis of change from baseline in average PEF.

Further details on the models for secondary endpoints will be provided in the SAP.

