4.6.1 Baseline, Change from Baseline and Percentage Change from Baseline Definitions

In general, the baseline which will be used in calculation of change from baseline will be the last value obtained before first study intervention.

Exceptions to the general definition of baseline (for calculation of change from baseline) are the following:

- In-clinic FeNO test: baseline is defined as the mean of measurements at Day -1 and at Day 1 morning pre-dose at Visit 3 in Part 1 and as Day 1 morning pre-dose at Visit 3 in Part 2.
- FeNO at home assessments: baseline is defined as the mean of all available measurements during the 7 days period prior to Day 1 in Part 1.
- In-clinic pre-bronchodilator FEV₁, FVC and FEV₁/FVC in absolute values and in percent of predicted values: baseline for Part 1 is the mean of measurements at Day -1 and at Day 1 morning pre-dose at Visit 3; for Part 2 is the pre-bronchodilator assessment at Visit 1.
- In-clinic FEV₁ is the mean of Day -1 and Day 1 morning pre-dose at Visit 3 for Part 1 and is the mean of measurements at Day 1 pre-dose timepoints (15 and 45 minutes pre-dose) for Part 2.
- In-clinic post-bronchodilator FEV₁, FVC and FEV₁/FVC in absolute values and in percent of predicted values: baseline is the measurement at Visit 1 (1 measurement) within performed 15 to 30 minutes after inhalation of 400 µg of salbutamol.
- FEV₁ home spirometry: baseline is defined as the mean of all available measurements during the 7 days period prior to Day 1 in both Part 1 and Part 2. i.e. The baseline for the morning assessments will be: the mean of all available morning measurements in the 7 days period prior to Day 1. Same approach will be used for the baseline for the evening assessments.
- e-Diary variables (cough VAS, **CCI** [REDACTED], evening PEF, daily asthma symptom score): baseline is average over measurements on the 7 days prior to randomisation. For the morning assessments of PEF, daily use of rescue medication and asthma symptoms the baseline is average over morning assessments from Day -6 to Day -1 and the Day 1 pre-dose assessment.

For e-Diary any study day will be derived relative to randomisation.

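### SAP 4.12.4 does not name the baseline covariate for the log-FeNO model; read literally, it is baseline FEV1, which costs some precision

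*SAP*

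**What the plan says.** SAP 4.12.4 defines the FeNO model in one sentence: "The analysis of change from baseline in log transformed FeNO will be performed as described for the primary endpoint in Section 4.11". It then lists what changes for FeNO: natural log scale, back-transformation, and results as geometric least-squares means and their ratios. A change of covariate is not on that list.

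The model in SAP 4.11 has treatment group, week, and "country, baseline FEV₁, and treatment-by-week interaction as fixed effects and with participant as random effect". Its responses are the values at Weeks 1 to 4 (Visits 4 to 7).

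Protocol 9.4.2.2 is looser: "Similar MMRM as for the primary variable will be used for analysis of change from baseline in ACQ-6 and in FeNO". It passes the detail on: "Further details on the models for secondary endpoints will be provided in the SAP". For PEF, the same section specifies an ANCOVA that also has terms for treatment and country: "and baseline as covariate will be used for the analysis of change from baseline in average PEF".

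The protocol's own primary model (9.4.2.1) also carries an eosinophil count group, but not FeNO. SAP 4.6.1 does define an in-clinic FeNO baseline, "as Day 1 morning pre-dose at Visit 3 in Part 2".

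**The concern.** Protocol 9.4.2.2 hands the specification to the SAP, and the SAP hands it to a model built for another variable. A programmer working from SAP 4.12.4 alone would regress the change in log FeNO on baseline FEV1.

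The unstructured covariance would not recover what is lost, because baseline FeNO is not among the modelled responses. It enters only through the change score, with its coefficient fixed at 1.

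This matters a little more than usual because the current SAP makes ACQ-6, PEF and the symptom score descriptive (4.12.2 and 4.12.3). Apart from the FEV1 average, FeNO is the only secondary efficacy variable with a fitted model, confidence intervals and treatment contrasts. At stake are the width of those intervals, protection against chance baseline imbalance, and a covariate choice that would otherwise stay open until the analysis is programmed.

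**Working it through.** **The plan's own figure.** The only sample-size figure is 73 evaluable per arm, for FEV1 (SAP 4.19: one-sided 5%, difference 175 mL). Power and SD are blacked out, so it cannot be reproduced. Solving SD = 175 × √(73/2) / (z₀.₉₅ + z_power) gives 425 mL at 80% power and 361 mL at 90%. Neither bears on FeNO, for which no power, SD, correlation or n is stated. I use 73 per arm below only as a convenient size.

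**Inputs that must be assumed.** ρ is the correlation between baseline and Week-4 log FeNO, taken as 0.5 to 0.9. Before selection, the log-scale SD is 0.5 to 0.7 and the median 30 to 40 ppb. Country and baseline FEV1 are taken to carry no information about FeNO change. The comparison is Week 4 only.

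**Step 1: no selection.** With equal variances σ² at both times:
- change score without its own baseline: 2σ²(1 − ρ)
- change score adjusted for its own baseline: σ²(1 − ρ²)
- variance ratio: 2/(1 + ρ)

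**Step 2: with the entry requirement.** Protocol 5.1.2 and 5.1.4 require FeNO of at least 25 ppb at Visit 1 and again at Visit 3, the visit that supplies the baseline. This narrows the baseline range and so reduces what adjustment can recover. I simulated log FeNO at Visit 1, Day 1 and Week 4 as multivariate normal with equal correlations (400,000 draws per setting), kept those at or above 25 ppb at both earlier times, and compared the variance of the change with its residual variance after regression on baseline. Ranges are over the two medians and two SDs.

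| ρ | Variance ratio, no selection | SE ratio, no selection | Variance ratio, ≥ 25 ppb | SE ratio, ≥ 25 ppb | 73 per arm acts like (≥ 25 ppb) |
|---|---|---|---|---|---|
| 0.5 | 1.333 | 1.155 | 1.205–1.251 | 1.098–1.118 | 58–61 |
| 0.7 | 1.176 | 1.085 | 1.135–1.153 | 1.065–1.074 | 63–64 |
| 0.8 | 1.111 | 1.054 | 1.097–1.103 | 1.047–1.050 | 66–67 |
| 0.9 | 1.053 | 1.026 | 1.051–1.053 | 1.025–1.026 | 69 |

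The last column is 73 divided by the variance ratio; for example, 73/1.251 = 58.4.

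**Step 3: chance imbalance.** A one-standard-error baseline difference shifts the log ratio by √(SD²_change − SD²_adjusted) × √(2/73), where √(2/73) = 0.1655. From the selected simulations:
- smallest (ρ = 0.8, median 30, SD 0.5): √(0.306² − 0.292²) × 0.1655 = 0.0915 × 0.1655 = 0.015, about 1.5%
- largest (ρ = 0.5, median 40, SD 0.7): √(0.659² − 0.593²) × 0.1655 = 0.2875 × 0.1655 = 0.048, about 5%

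**The case against.** The strongest reply is that the sponsor probably intends the swap. When a repeated-measures model is reused for a new response, the usual reading is that the new variable's own baseline comes with it. The protocol asks for a similar model, not an identical one, and its PEF wording suggests that own-baseline adjustment is the convention in this study. SAP 4.10.2, which lists country and baseline FEV1, is introduced by "The primary efficacy analysis for Part 2 will be adjusted for the following baseline covariates"; it does not extend to FeNO and cannot be cited for the literal reading. This reply stands. A reader might infer from SAP 4.12.4 that the FeNO analysis is definitely not adjusted for baseline FeNO, but no passage says that baseline FeNO is left out or that baseline FEV1 is kept. The documents support only that the covariate is unstated and that the literal text points to FEV1.

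A reader might also infer that selection on the baseline reading biases the comparison through regression to the mean. It does not: the selection applies equally to both randomised arms.

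The untruncated formula gives a 15% larger standard error and an effective 55 per arm at ρ = 0.5. Those figures ignore the 25 ppb requirement and are too pessimistic.

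Finally, FeNO is a secondary endpoint in a Phase IIa trial with no multiplicity adjustment, so the consequence is limited. That is fair, but it does not remove the gap: the protocol says the SAP will supply the model detail, and the SAP does not.

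**Conclusion.** The specification gap is established from the text. The loss of precision is conditional on the literal reading. On that reading the analysis is valid: the outcome is already a log ratio to baseline, and the between-arm ratio is unbiased over randomisation. It is less efficient than it need be, with a standard error about 5% to 12% larger for ρ of 0.8 to 0.5, and only about 3% larger at 0.9. A one-standard-error chance imbalance would move the ratio by roughly 1.5% to 5% for ρ of 0.8 to 0.5.

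Every figure rests on the assumed correlation, SD and median, none of which the documents give. The direction holds for any correlation below 1 under the equal-variance model of Step 1. This is a modest improvement at almost no cost, not a threat to the trial's primary conclusion.

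**What to change.** In SAP 4.12.4, state that the model is the MMRM of Section 4.11 with baseline log FeNO (Day 1 pre-dose, Visit 3) replacing baseline FEV1, all other terms unchanged, for both the Week 4 and the treatment-period average contrasts. Fix this before unblinding; under SAP Section 1, a change made before database lock goes into a new SAP version.

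The cost is one clause and one model term. The baseline value is already collected and defined. No participant is lost by adding it, because under SAP 4.6.1 a missing baseline already makes the change from baseline missing. If the sponsor does want baseline FEV1 in the FeNO model, it should say so and add baseline log FeNO alongside it.
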